12.7 Laboratory and instrumental examinations to be documented in the study

All examinations (physical examination and vital signs, laboratory tests and other exams) will be performed in accordance with common clinical routine practice, routine practice of a particular medical institution. All examinations are solely based on the physician's decision about strategy of diagnostics and treatment.

The following laboratory and instrumental examinations are planned to collect in the study:

- Laboratory tests results
 - Biomarkers: CRP, faecal calprotectin
 - Immunological tests: TB diagnostic test
- Endoscopic examination/ biopsy of GI tract
- X-ray of GI tract and lungs
- MRI/CT examination related to IBD
- Ultrasound examination related to IBD

All laboratory and instrumental examinations are collected during all period of data collection: retrospectively, at Baseline visit, through 1 year of prospective observation.

12.8 Documentation of Medical history and Concurrent Medical Conditions.

Medical history is history of diseases indicated before signing of the Informed Consent Form.

Concurrent medical conditions are those significant (ongoing conditions or diseases that are present at signing of informed consent). Concurrent medical conditions may include not limited to tuberculosis, cardiovascular disorders, diabetes, chronic pulmonary artery disease, chronic kidney disease. The condition (i.e., diagnosis) should be registered in eCRF.

Time of medical event/disease	How it should be documented
Before ICF signed	Medical history
At the moment of ICF signing	Concurrent medical conditions
After ICF signing	Adverse Events

12.9 Healthcare resources utilization (HCRU)

Resource utilization will be captured from the patients' medical records:

HCRU will be calculated for hospitalizations related to IBD complications, IBD-related surgeries as available in the medical record and captured in the eCRF.

12.10 Physician Survey

The survey assessed the duration and nature of clinicians' IBD clinical practice, and familiarity with a treat-to-target approach to UC/CD management and its perceived relevance will be explored. Clinicians' perceptions of their current use of objective measures of disease activity to guide management, optimal treatment targets in UC/CD, and the proportion of their patients in which these targets are currently achieved were evaluated.

13 Safety Reporting

13.1 Definitions

13.1.1 Adverse Event and Adverse Drug Reactions

An **Adverse Event (AE)** is defined as any any untoward medical occurrence in a patient administered a medicinal product and which does not necessarily have a causal relationship with this treatment.

An AE can be any unfavorable and unintended sign (e.g. an abnormal laboratory finding), symptom or disease, occurring after exposure to the drug, whether or not considered related to the medicinal product.

An **Adverse drug reaction (ADR)** is an unintentional, unfavorable reaction of the human body associated with the use of a medicinal (investigational) product and involving at least a possible relationship with the use of the suspected medicinal (investigational) product

13.1.2 Additional Points to Consider for AEs/ADRs

An untoward finding generally may:

- Indicate a new diagnosis or unexpected worsening of a pre-existing condition. (Intermittent events for pre-existing conditions underlying disease should not be considered AEs/ADRs.)
- Necessitate therapeutic intervention.
- Require an invasive diagnostic procedure.
- Require discontinuation or a change in dose of study medication or a concomitant medication.
- Be considered unfavorable by the investigator for any reason.

Diagnoses vs signs and symptoms:

- Each event should be recorded to represent a single diagnosis. Accompanying signs (including abnormal laboratory values or ECG findings) or symptoms should NOT be recorded as additional AEs/ADRs. If a diagnosis is unknown, sign(s) or symptom(s) should be recorded appropriately as an AE(s)/ADRs.

Laboratory values:

- Changes in laboratory values are only considered to be AEs/ADRs if they are judged to be clinically significant (i.e., if some action or intervention is required or if the investigator judges the change to be beyond the range of normal physiologic fluctuation). A laboratory re-test and/or continued monitoring of an abnormal value are not considered an intervention. In addition, repeated or additional noninvasive testing for verification, evaluation or monitoring of an abnormality is not considered an intervention.
- If abnormal laboratory values are the result of pathology for which there is an overall diagnosis (e.g., increased creatinine in renal failure), the diagnosis only should be reported appropriately as an AE/ADRs.

Pre-existing conditions:

- Pre-existing conditions (present at the time of signing of informed consent) are considered concurrent medical conditions and should NOT be recorded as AEs/ADRs. However, if the patient experiences a worsening or complication of such a concurrent condition, the worsening or complication should be recorded as an AE/ADRs (worsening or complication occurs after start of study medication). Investigators should ensure that the event term recorded captures the change in the condition (e.g., “worsening of...”).
- If a patient has a pre-existing episodic condition (e.g., asthma, epilepsy) any occurrence of an episode should only be captured as a AE/ADRs if the episodes become more frequent,

serious or severe in nature, that is, investigators should ensure that the AE/ADR term recorded captures the change in the condition from Baseline (e.g. “worsening of...”).

- If a patient has a degenerative concurrent condition (e.g., cataracts, rheumatoid arthritis), worsening of the condition should only be captured as an AE/ADR if occurring to a greater extent to that which would be expected. Again, investigators should ensure that the AE term recorded captures the change in the condition (e.g., “worsening of...”).

Worsening of AEs/ADRs:

- If the patient experiences a worsening or complication of an AE/ADR after any change in study medication, the worsening or complication should be recorded as a new AE/ADR. Investigators should ensure that the AE/ADR term recorded captures the change in the condition (eg, “worsening of...”).

Changes in severity of AEs/ADRs:

- If the patient experiences changes in severity of AE/ADRs, the event should be captured once with the maximum severity recorded.

Preplanned surgeries or procedures:

- Preplanned procedures (surgeries or therapies) that were scheduled prior to signing of informed consent are not considered AEs/ADRs. However, if a preplanned procedure is performed early (e.g., as an emergency) due to a worsening of the pre-existing condition, the worsening of the condition should be captured appropriately as an AE/ADRs. Complications resulting from any planned surgery should be reported as AEs/ADRs.

Elective surgeries or procedures:

- Elective procedures performed where there is no change in the patient’s medical condition should not be recorded as AEs/ADRs. Complications resulting from an elective surgery should be reported as AEs/ADRs.

Insufficient clinical response (lack of efficacy):

- Insufficient clinical response, efficacy, or pharmacologic action should NOT be recorded as an AE/ADR. The investigator must make the distinction between exacerbation of pre-existing illness and lack of therapeutic efficacy.

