11.1 Inclusion Criteria

Every eligible patient at participating investigational sites must meet the following criteria:

Inclusion criteria:

1. Male and female patients 18 years or older by the time of enrolment
2. Confirmed diagnosis of Crohn's disease or ulcerative colitis for at least 2 years prior to enrolment in the study.
3. The presence of a moderate to severe IBD flare at the time of enrolment or in patient anamnesis within 2 years before enrollment treated with steroids or/ and immunosuppressive agents or/ and biologic therapy. IBD flare(s) must be confirmed in the source documentation.
4. Current treatment with steroids or/ and immunosuppressive agents or/ and 5-ASA or/ and biologic therapy
5. Written informed consent, signed before the participation in the study begins.

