#### 8.1.5 Safety data analysis

Collection of safety data starts with the signing of ICF for this study, so, there will be no safety data available for the retrospective part of the study.

Protocol ID	MACS-2017-102279	STATISTICAL ANALYSIS PLAN	Page 27 of 41	
IP	N/A		Date	30.12.2021
ID	MACS-2017-102279_SAP		Version	v1.2 final

Safety data will be presented for the population of all patients enrolled as well as for each defined treatment combination (or pattern, if applicable) separately. Data will be presented as total counts as well as distribution by SOC at Visits 1, 2 and 3:

- Overall frequency of all AEs;
- Frequency of all AEs that led to treatment discontinuation / treatment change regardless of their relation to a particular medication;
- Frequency of SAEs;
- Frequency of all SAEs that led to treatment discontinuation / treatment change regardless of their relation to a particular medication;
- Frequency of ADRs;
- Frequency of SADRs;
- Frequency of pregnancy cases.

Additionally, all AEs/SAEs and ADRs/SADRs will be tabulated according to their relation to a particular medication (see example Table 17), separate tables will be generated for each medication being a monotherapy and in treatment combination.

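### Protocol 13.1.2 has no IBD-specific recording rule and its general rules pull apart for a flare on treatment, so the all-cause AE/SAE rows in SAP 8.1.5 can vary with the investigator

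*Protocol*

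**What the plan says.** IBD is a pre-existing condition in every patient. Protocol 11.1 requires "Confirmed diagnosis of Crohn's disease or ulcerative colitis for at least 2 years prior to enrolment in the study". The rules of Protocol 13.1.2 for pre-existing conditions therefore bear on the disease under study itself.

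That section contains five statements that can reach an IBD flare:

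- Worsening of a condition present at consent: "if the patient experiences a worsening or complication of such a concurrent condition, the worsening or complication should be recorded as an AE/ADRs".
- Underlying disease: "Intermittent events for pre-existing conditions underlying disease should not be considered AEs/ADRs".
- Episodic condition: "any occurrence of an episode should only be captured as a AE/ADRs if the episodes become more frequent", or more serious or severe. The examples given are asthma and epilepsy.
- Lack of efficacy: "Insufficient clinical response, efficacy, or pharmacologic action should NOT be recorded as an AE/ADR".
- Who decides: "The investigator must make the distinction between exacerbation of pre-existing illness and lack of therapeutic efficacy".

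Protocol 13.1.3 makes an adverse event serious if it requires admission to hospital. SAP 8.1.5 tabulates, for all patients enrolled and for each treatment combination, all AEs, AEs leading to discontinuation or change, SAEs, and "Frequency of all SAEs that led to treatment discontinuation / treatment change regardless of their relation to a particular medication". The tables are split by system organ class. No separate line is planned for IBD events.

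**The concern.** Patients are enrolled because of a moderate to severe flare, current or within the previous two years, and are then followed on treatment for about a year. Further flares, some with admission, are to be expected. If the recording rule for such a flare is unsettled, the all-cause AE and SAE frequencies depend partly on how each investigator at about 35 sites reads 13.1.2. Because 8.1.5 shows these frequencies by treatment combination, a difference in recording habit between sites that favour different drugs could be read as a difference in safety.

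Collection also differs by drug. Under Protocol 13.2.3 all AEs are collected on vedolizumab, but only ADRs and SAEs on other IBD treatments. For flares that are neither serious nor judged drug-related, the recording question therefore arises on one drug only.

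**Working it through.** The plan states no figure on this point, so the check is to apply the text to a case and then illustrate the possible size.

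**Case 1: a UC patient in remission on a biologic relapses and is admitted.**

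- Worsening rule: recorded as an AE. Admission makes it serious under 13.1.3. Count 1.
- Episodic rule: recorded only if episodes have become more frequent, serious or severe. No reference period or threshold is given. Count 0 or 1.
- Underlying-disease exclusion: Protocol 4.2 describes IBD as alternating periods of active and quiet disease, so a relapse fits an intermittent event. Count 0.
- Lack-of-efficacy exclusion: Protocol 4.2 defines a flare as arising from remission, including remission reached through medical treatment. In a treated patient the same relapse can be described as loss of response. Count 0.

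The investigator chooses between the last reading and an exacerbation without a stated criterion.

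**Case 2: a complication of IBD.** The worsening rule expressly calls for recording, and no sentence expressly forbids it. It drops out only if someone reclassifies it as an intermittent event or as lack of efficacy.

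**Which outputs are reached.**

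- The all-cause AE and SAE rows of SAP 8.1.5, including those leading to treatment change, carry no filter on relatedness. They are exposed.
- The safety outcome in Protocol 6.2 and SAP 7.1 covers SAEs related to IBD treatment. A flare judged unrelated does not enter it. The protection is partial, because Protocol 13.1.5 mentions underlying disease in the definitions of both Related and Not Related.
- SAEs that have nothing to do with IBD are not exposed.

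**Illustration of size.** All rates here are assumed; none is in the documents. Let b be the share of patients with another SAE, f the share with an IBD admission, and s the share of those admissions recorded as SAEs. With independence,

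P(any SAE) = 1 − (1 − b)(1 − f·s).

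| b | f | s = 0 | s = 1 | ratio |
|---|---|---|---|---|
| 3% | 8% | 3.0% | 1 − 0.97×0.92 = 10.8% | 3.6 |
| 3% | 15% | 3.0% | 1 − 0.97×0.85 = 17.6% | 5.9 |
| 5% | 8% | 5.0% | 1 − 0.95×0.92 = 12.6% | 2.5 |
| 5% | 15% | 5.0% | 1 − 0.95×0.85 = 19.3% | 3.9 |

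No recording and full recording are the two extremes. With b = 5% and f = 10%, the frequency is 5.0% at s = 0, 9.8% at s = 0.5 and 14.5% at s = 1. For 2000 patients the 95% half-width, 1.96·√(p(1−p)/2000), is about 1.0 point at 5% and 1.5 points at 14.5%. On these assumptions the recording choice could exceed sampling error in the whole cohort. Single treatment combinations are smaller, so their sampling error is larger.

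**The case against.** The strongest reply is that 13.1.2 can be read as one conditional rule. A usual relapse is not an event; a relapse that is more frequent, serious or severe than before is. A reader might infer that the protocol flatly requires and forbids recording the same flare. Once the episodic rule is counted, the documents do not support that. What stands is narrower: the episodic rule does not name IBD or set a comparison period, and nothing says that it overrides the worsening rule or the two exclusions.

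A reader might also treat exacerbation and lack of efficacy as always the same event. They are not. The protocol's flare starts from remission, so it differs from primary non-response; the overlap lies in secondary loss of response.

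Some protection exists already. Investigators are trained towards a common reading of the protocol (Protocol 14.1.1). Exacerbations, complications, surgery and hospitalisations due to complications are tabulated by treatment combination whatever their AE status (SAP 8.1.3). SAP 8.1.5 also shows SADRs and events by relation to each medication, and all data are listed. These limit the harm. They do not give the all-cause rows a common rule, and a system organ class does not isolate IBD events. Variation between sites is a risk inferred from the text, not something the documents show.

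One might also expect the row of SAEs leading to treatment change to repeat most of the treatment-failure outcome. That is unsupported: failure includes dose escalation, switching and augmentation, none of which needs a serious event.

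**Conclusion.** The point holds in a limited form. For an IBD flare on treatment, 13.1.2 gives no disease-specific rule, its general rules lead to different answers, and the deciding judgement has no criterion. The all-cause AE and SAE rows of SAP 8.1.5 are therefore open to variation between investigators. Complications are affected only through reclassification, and the treatment-related SAE outcome only through the causality judgement.

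It would go too far to say that the SAE frequency has no fixed meaning, since its non-IBD part is unaffected. Nor does a fixed multiplier follow. The ratio of about 2.5 to 5.9 rests on assumed rates, on independence, and on comparing no recording with complete recording; the true size is unknown. The analysis is descriptive, so no test is at risk. What is at risk is a misreading of SAE frequency across treatments.

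**What to change.** Reconcile the sentences of Protocol 13.1.2 as they apply to IBD flares and complications. This settles the intended reading but will probably not change the data: the SAP is dated 30.12.2021, after the planned last patient visit in Q2-Q3 2021.

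The table split therefore does most of the work. In SAP 8.1.5, tabulate AEs and SAEs in two blocks by MedDRA term: IBD flare, complication or surgery, and all other events. List the terms that define the first block. Read the second block when describing safety across treatments, since it is largely free of the ambiguity.

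State two limits in the report. Flares never recorded as AEs cannot be recovered by the split. The healthcare-utilisation tables do not fill that gap, because Protocol 12.9 covers hospitalisations related to IBD complications and IBD-related surgeries, not every flare admission.

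The cost is a clarifying statement and one extra split in the safety tables. Adverse events are already to be MedDRA-coded, so no new data are needed.

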13.1.3 Serious AEs

A serious AE (SAE) is any AE which results in death, is life threatening, requires inpatient hospitalisation or prolongation of existing hospitalisation, results in persistent or significant disability or incapacity, or is a congenital anomaly or birth defect.

A serious AE are defined as any untoward medical occurrence that at any dose:

1. Results in DEATH.
2. Is LIFE THREATENING.

The term “life threatening” refers to an event in which the patient was at risk of death at the time of the event; it does not refer to an event that hypothetically might have caused death if it were more severe.

3. Requires inpatient HOSPITALIZATION or prolongation of existing hospitalization.
4. Results in persistent or significant DISABILITY/INCAPACITY.
5. Leads to a CONGENITAL ANOMALY/BIRTH DEFECT.
6. Is an OTHER IMPORTANT MEDICAL EVENT that satisfies any of the following:
 - May require intervention to prevent items 1 through 5 above.
 - May expose the patient to danger, even though the event is not immediately life threatening or fatal or does not result in hospitalization.
 - Includes any event or synonym described in the Takeda Medically Significant AE List.

Table 10.a Takeda Medically Significant AE List

Term	
Acute respiratory failure/acute respiratory distress syndrome	Hepatic necrosis
Torsade de pointes/ventricular fibrillation/ventricular tachycardia	Acute liver failure
Malignant hypertension	Anaphylactic shock
Convulsive seizure	Acute renal failure
Agranulocytosis	Pulmonary hypertension
Aplastic anemia	Pulmonary fibrosis
Toxic epidermal necrolysis/Stevens-Johnson syndrome	Confirmed or suspected endotoxin shock
	Confirmed or suspected transmission of infectious agent by a medicinal product
	Neuroleptic malignant syndrome / malignant hyperthermia
	Spontaneous abortion / stillbirth and fetal death

Note: Terms identified on the Medically Significant AE List represent the broad medical concepts to be considered as “Important Medical Events” satisfying SAE reporting requirements.

Medical and scientific judgement should be exercised in deciding whether other situations should be considered serious, such as important medical events that might not be immediately life-threatening or result in death or hospitalisation but might jeopardise the patient or might require intervention to prevent one of the other outcomes listed above. Examples of such events are intensive treatment in an emergency room or at home for allergic bronchospasm, blood dyscrasias or convulsions that do not result in hospitalisation, or development of dependency or abuse.

Any suspected transmission of an infectious agent via a medicinal product is considered a serious adverse reaction.

13.1.4 Severity AEs/ADRs

The different categories of intensity (severity) are characterized as follows:

Mild: The event is transient and easily tolerated by the patient.

Moderate: The event causes the patient discomfort and interrupts the patient's usual activities.

Severe: The event causes considerable interference with the patient's usual activities.

13.1.5 Causality of AEs/ADRs

The relationship of each AE/ADR to study medication will be assessed using the following categories:

Related: An AE/ADR that follows a reasonable temporal sequence from administration of a drug (including the course after withdrawal of the drug), or for which possible involvement of the drug cannot be ruled out, although factors other than the drug, such as underlying diseases, complications, concomitant drugs and concurrent treatments, may also be responsible.

Not Related: An AE/ADR that does not follow a reasonable temporal sequence from administration of a drug and/or that can reasonably be explained by other factors, such as underlying diseases, complications, concomitant drugs and concurrent treatments.

13.1.6 Start and Stop Dates

The start date of the AE/ADR is the date that the first signs/symptoms were noted by the patient and/or physician.

The stop date of the AE/ADR is the date at which the patient recovered, the event resolved but with sequel or the patient died. If AE/ADR is ongoing at the moment of end of observation, it should be indicated in the eCRF.

13.1.7 Frequency

AEs/ADRs (e.g., vomiting) or those which occur repeatedly over a period of consecutive days are *intermittent*. All other events are *continuous*.

13.1.8 Action Concerning Study Medication

- *Drug withdrawn* – a study medication is stopped due to the particular AE/ADR.
- *Dose reduced* - the dose was reduced due to the particular AE/ADR.
- *Dose Increased* – the dose was increased due to the particular AE/ADR
- *Dose not changed* – the particular AE/ADR did not require stopping a study medication.

- *Dose Interrupted* – the dose was interrupted due to the particular AE/ADR
- *Unknown* – only to be used if it has not been possible to determine what action has been taken.

13.1.9 Outcomes of AEs/ADRs

- *Fatal*: The patient died due to the AE/ADR. If the patient died due to other circumstances than the AE/ADR the outcome should be stated as ‘Not recovered’ or ‘Recovering’. The date of death will be recorded.
- *Recovered/Resolved*: The patient has fully recovered from the event or the condition has returned to the level observed at baseline
- *Recovering/Resolving*: The event is improving but the patient is still not fully recovered
- *Not Recovered/Not Resolved*: The event is ongoing at the time of reporting and the patient has still not recovered
- *Recovered with Sequelae/Resolved with Sequelae*: As a result of the event, the patient suffered persistent and significant disability/incapacity (e.g. became blind, deaf or paralysed).
- *Unknown*: If Outcome is not known or not reported.

